#### 8.1.6 Efficacy Analysis

Efficacy analysis will be performed for all patients enrolled on the study in the full analysis set.

##### Response

Parameters assessed will include stringent complete response (sCR), complete response (CR), very good partial response (VGPR), partial response (PR), and stable disease (SD) per standard IMWG response criteria. In addition, overall response rate (defined as greater than or equal to PR across all cycles of treatment), response duration, time-to-response (TTR), MRD negativity rate and improvement in response during maintenance therapy will be assessed.

Best overall response categories will be tabulated and overall for CR, VGPR, PR, SD, progressive disease, and relapse. A two-sided 95% exact binominal CI will be calculated for each category. The response rate (responses  $\geq$  PR) will also be tabulated. Time-to-event analyses will be done using Kaplan- Meier analyses and will include time to response, duration of response, PFS, and OS, as data allow. If there is not enough data to apply the Kaplan-Meier test, the data will be summarized by descriptive statistics.

Time to response (for responders only) will be calculated as the time from the date of first study treatment dosing to the first date of documented response (PR or better) and will be summarized by descriptive statistics.

Duration of response (for responders only) is defined as the time from the earliest date of documented response (PR or better) to the earliest date when disease progression was confirmed. Patients who are non-responders will be excluded from this analysis. Detailed censoring rules for duration of response will be specified in the SAP.

PFS will be calculated as the time from the initial administration of Daratumumab, Clarithromycin, Pomalidomide, and Dexamethasone until documented disease progression, as determined using standard response criteria, or death from any cause, whichever occurs first. Kaplan-Meier methods will be used to estimate PFS over time and the median duration of PFS. Patients with no PFS event will be censored at the date of their last disease assessment.

Time to next therapy is defined as the time from the initial administration of Daratumumab, Clarithromycin, Pomalidomide, and Dexamethasone on trial to next treatment.

OS is defined as the time from the initial administration of Daratumumab, Clarithromycin Pomalidomide and Dexamethasone to death from any cause. Kaplan-Meier methods will be used to estimate the OS function. Patients who do not die will be censored at the date that the patient was last known to be alive.

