## 8. STATISTICAL AND QUANTITATIVE ANALYSES

### 8.1 Statistical Methods

The primary endpoint will be the  $\geq$  VGPR response proportion as best response within the first 8 cycles of treatment. Based on historical data, the  $\geq$  VGPR response proportion is approximately 9%; therefore, the target  $\geq$  VGPR response proportion will be  $\geq$  25%.

This exact single-stage design yields a  $\geq$  0.80 probability of a positive result if the true  $\geq$  VGPR response proportion is  $\geq$  25%. It yields a  $\geq$  0.95 probability of a negative result if the true  $\geq$  VGPR response proportion is  $\leq$  9%. A 95% confidence interval constructed around the expected  $\geq$  VGPR response proportion of 25% can be estimated to be within  $\pm$  17.9% of the observed  $\geq$  VGPR response proportion.

Analysis Plan for Endpoints:

Primary Endpoint:

The primary endpoint is the  $\geq$  VGPR response proportion as best response within the first 8 cycles of treatment; A 95% confidence interval will be estimated for the  $\geq$  VGPR response proportion via binomial proportions.

Secondary endpoints:

Secondary endpoints include median PFS, OS, time to response and progression, DoR, TTNT, ORR, VGPR rate, CR or better rate, improvement in response rate during maintenance therapy and MRD negativity rate. Median PFS/OS, including survival curves, will be estimated using Kaplan-Meier methodology. Greenwood's formula will be used to calculate 95% confidence intervals for the Kaplan-Meier survival estimates.

All analyses will be performed in SAS Version 9.4 (SAS Institute, Inc., Cary, North Carolina) and Stata Version 15.0 (StataCorp, College Station, Texas).

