### 8.1.4 Procedures for Handling Missing, Unused, and Spurious Data

Every effort must be made to avoid missing data. For all time-to-event endpoints, patients who do not have the event of interest will be censored at the date at which they were last known to be event-free. Missing data for quantitative endpoints will be replaced by the patient's last available value. Additional approaches for sensitivity analyses of the effects of missing data for secondary endpoints may be provided in the SAP.

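### Section 8.1.6 lets PFS, OS and duration of response drop from Kaplan-Meier to unspecified descriptive statistics when data are judged too few, with no trigger defined and against the plan's own Kaplan-Meier and censoring statements

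*Combined protocol and SAP*

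**What the plan says.** Section 8.1.6 (Response) states that the Kaplan-Meier analyses "will include time to response, duration of response, PFS, and OS, as data allow". The next sentence is the fallback: "If there is not enough data to apply the Kaplan-Meier test, the data will be summarized by descriptive statistics". It sets no number of events or patients, names no statistic and does not mention censored patients.

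Other parts of the plan treat the same endpoints without that condition:

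- Section 8.1, repeated in the Protocol Summary under Endpoints: "Median PFS/OS, including survival curves, will be estimated using Kaplan-Meier methodology", with Greenwood confidence intervals.
- Section 8.1.4, as the general rule for censoring: "patients who do not have the event of interest will be censored at the date at which they were last known to be event-free".
- Section 8.1.6, PFS: Kaplan-Meier for the curve and the median, and "Patients with no PFS event will be censored at the date of their last disease assessment".
- Section 8.1.6, OS: Kaplan-Meier for the survival function, and "Patients who do not die will be censored at the date that the patient was last known to be alive".
- Section 8.1.6, duration of response: "Detailed censoring rules for duration of response will be specified in the SAP".

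The other use of descriptive statistics in that subsection is for time to response, in responders only, measured from first dosing "to the first date of documented response (PR or better) and will be summarized by descriptive statistics".

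**The concern.** The fallback solves no real problem. A Kaplan-Meier curve can be computed with any number of events. When events are few the curve stays above 50% and the median is reported as not reached, which is itself the correct result.

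The fallback would come into play when events are sparse and many patients are still being followed. A plain summary of times is least reliable there. Counting censored times as if they were events, or using only the patients with events, produces a median that mostly reflects length of follow-up.

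Because no trigger is defined, the choice between the two methods can also be made after the data are seen. Median PFS and OS are named secondary outcomes of a single-arm trial. Readers are likely to set them beside the medians in section 1.1, although the plan schedules no such comparison.

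**Working it through.** **Figures in the plan.** No number is given for the fallback or for the precision of any time-to-event endpoint. The only sizing rule is 8 or more of 40 patients with VGPR or better (section 8.1.1). For X binomial with n = 40, P(X ≥ 8 | 0.09) = 0.024 and P(X ≥ 8 | 0.25) = 0.818. This agrees with the stated bounds (at least 0.95 probability of a negative result at 9%, at least 0.80 of a positive one at 25%), and the fallback does not touch it.

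**Inputs.** N = 40 (section 4.2). True medians are taken, as an assumption, from section 1.1: PFS 7.7, duration of response 9.3 and OS 19.3 months (ClaPd), and PFS 8.8 months (daratumumab with pomalidomide and dexamethasone). The documents give no accrual period. Uniform accrual over 24 months is assumed and varied from 12 to 36. Event times are assumed exponential, with rate λ = ln 2 / median.

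**A case that can be checked by hand.** Take OS with the data cut at the end of a 24-month accrual.

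- λ = 0.6931 / 19.3 = 0.0359 per month.
- Expected deaths = 40 × [1 − (1 − e^(−24λ)) / (24λ)] = 40 × [1 − 0.578 / 0.862] = 13.2.
- If censoring is ignored, the median of all observed times solves e^(−λx) × (1 − x/24) = 0.5. At x = 8.0 this is 0.750 × 0.667 = 0.500. The descriptive median is therefore 8.0 months against a true 19.3.
- By simulation, the median among deaths only is 5.7 months. The Kaplan-Meier median is about 19.4 and is reached in about 62% of runs; in the rest it is correctly not reached.

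**Sparse to mature data.** The simulation uses 24-month accrual and cuts the data at the k-th event. Entries are medians over runs, in months. In the Kaplan-Meier column, runs without a median count as infinite.

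| True median | Events | All times, censoring ignored | Events only | Kaplan-Meier (share of runs reaching a median) |
|---|---|---|---|---|
| 7.7 | 10 | 4.0 (−49%) | 3.1 (−59%) | 7.5 |
| 8.8 | 5 | 3.3 (−62%) | 2.5 (−72%) | 9.0 (59%) |
| 8.8 | 10 | 4.3 (−51%) | 3.3 (−62%) | 8.6 (91%) |
| 8.8 | 20 | 5.4 (−38%) | 4.5 (−49%) | 8.7 (100%) |
| 8.8 | 30 | 8.1 (−8%) | 6.0 (−32%) | 8.6 (100%) |
| 19.3 | 5 | 5.3 (−73%) | 3.7 (−81%) | not reached (29%) |
| 19.3 | 10 | 7.2 (−63%) | 5.2 (−73%) | 20.9 (53%) |
| 19.3 | 20 | 13.0 (−32%) | 8.3 (−57%) | 19.1 (100%) |
| 19.3 | 30 | 19.1 (−1%) | 13.0 (−32%) | 18.4 (100%) |

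With 5 to 10 events the descriptive medians are 49% to 81% too low. Varying accrual from 12 to 36 months widens this to 43% to 86%. With 30 events the all-times bias is 0% to 17% over the same accrual range, while the events-only bias stays near 30%.

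**Duration of response.** With 24 responders (60% of 40, using the ClaPd response rate), true median 9.3 months and a cut at 24 months, the medians are 5.7 (all times), 4.7 (events only) and about 9.3 (Kaplan-Meier).

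**Can sparse data arise?** Section 8.1.7 stops the study once more than 4 deaths have occurred, whatever the enrolment. The OS row with 5 events shows that situation.

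**The case against.** **No biased median is promised.** The sentence does not say that a median will be computed, and event counts, numbers censored, range of follow-up and patient listings are also descriptive. None of these is biased. This stands. A reader might infer that the trial will report medians far below the truth, but the text does not support that. The bias is conditional on carrying out the fallback as a plain summary of times.

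**The specific statements may govern.** PFS and OS each have their own Kaplan-Meier and censoring sentence, so the fallback could be read as residual. That is a reasonable reading, but the plan does not say which sentence prevails. Duration of response has no such unconditional statement, and its censoring rules are deferred to the SAP.

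**The bias is not always large.** A reader might infer understatement by a factor of 2 or more throughout. That does not hold. With OS cut at 36 months the all-times median is 15.3, a factor of 19.3 / 15.3 = 1.26. For duration of response at 24 months it is 9.3 / 5.7 = 1.63. Neither would plausibly count as too little data, since Kaplan-Meier is estimable in both. The large figures belong to the sparse case. Section 7.4 provides survival follow-up of up to 10 years for patients who complete treatment, so mature OS data are possible.

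**No planned decision depends on it.** Section 4.1 sets VGPR or better against 9% and ORR against 60%. No test compares PFS, OS or duration of response with a historical median. This stands and limits the weight of the point.

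**Conclusion.** The concern holds as a defect in the analysis rule for secondary endpoints. The fallback has no trigger, no defined content and no statistical need. It sits against unconditional Kaplan-Meier statements for PFS and OS and a general censoring rule, and it leaves the method open until the data are seen.

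If implemented as a plain summary of times, it would give medians roughly 50% to 80% too low at 5 to 10 events. This rests on exponential times, 24-month uniform accrual and true medians of 7.7 to 19.3 months; none of these is a planning assumption in the documents. The bias fades as events accumulate, and there would be none if every patient summarised had already had the event. The VGPR decision rule is unaffected. The sentence should be changed, but it does not threaten the trial's main conclusion.

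**What to change.** Delete the fallback sentence in section 8.1.6, and the condition on data availability in the sentence before it. Replace them with wording such as:

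> *Kaplan-Meier estimates will be reported for PFS, OS, duration of response, time to progression and time to next therapy whatever the number of events. Where the median is not reached this will be stated, with its lower confidence limit if estimable, the numbers of events and of censored patients, and Kaplan-Meier estimates at fixed times (for example 6 and 12 months). Time to response will be summarised descriptively in responders.*

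Time to progression and time to next therapy are included because both are secondary endpoints (section 3.2) and neither is in the Kaplan-Meier list of 8.1.6. Descriptive statistics remain suitable for time to response in responders, where every patient has the event. The censoring rules for duration of response, deferred to the SAP, should be written at the same time.

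The cost is a few lines of text, with no extra patients, visits or data. The downside is that a median may have to be reported as not reached.

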#### 8.1.7 Futility Analysis and Stopping Rules

If  $>4$  deaths have been observed, regardless of how many patients have been enrolled at that point or by that time, the study will be stopped due to futility.

If Grade 3-4 infection rate >15% is seen, protocol enrollment will be put on hold and amendments for risk reduction will be implemented.

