In the relapsed/refractory setting, a Phase 2 study of Biaxin®, pomalidomide, and dexamethasone (ClAPd) was studied in 120 patients with median of 5 prior lines (84% lenalidomide refractory). An ORR of 60% with ≥VGPR 23%, median PFS and DoR 7.7 and 9.3 mos, respectively and median OS 19.3 mos was seen. No influence on PFS was seen with lenalidomide or lenalidomide/bortezomib refractoriness nor significant differences in PFS/OS between low and high-risk patients. The most common gr 3/4 AEs were neutropenia 47% (gr 4 14%), lymphopenia 37% (gr 4 6%) and thrombocytopenia 33% (gr 4 16%) with no grade 5 events and a discontinuation rate of 3%.

This study is intended to investigate the combination of daratumumab, clarithromycin (Biaxin®), pomalidomide and dexamethasone [D-ClAPd] in multiple myeloma patients who have relapsed or refractory MM and have been previously exposed to daratumumab. Primary

endpoint will be response rate to treatment. Secondary endpoints will include toxicity of the combination, time to maximum response, and time to disease progression.

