- SAEs were reported in 118 patients (49%); the most frequently reported was pneumonia (21 patients; 9%), anemia, bronchitis, thrombocytopenia, atrial fibrillation, upper respiratory tract infection (3% each), and pyrexia (2%).
- Grade 3 or 4 TEAEs were reported in 193 patients (79%); the most frequently reported Grade 3 or 4 TEAEs were thrombocytopenia (45%), anemia (15%), and neutropenia (13%).
- Infections or infestations were reported in 73% of patients. The most frequently reported were upper respiratory tract infection (30%), pneumonia (14%), and bronchitis (13%).

Among the 103 patients treated in Study MMY1001 with daratumumab in combination with pomalidomide and dexamethasone:

- TEAEs leading to discontinuation of study treatment were reported in 15 patients (15%).
- Nine deaths (9%) were reported during study treatment or within 30 days after the last dose. Six patients died due to TEAEs; 2 patients died due to disease progression; and 1 patient died due to unknown reason.
- The most frequently reported TEAEs (reported in  $\geq 25\%$  of patients) were neutropenia (80%), anemia (54%), fatigue (52%), diarrhea (43%), thrombocytopenia (42%), cough (38%), dyspnea (32%), pyrexia (30%), leukopenia (37%), constipation (34%), nausea (31%), upper respiratory tract infection (28%), back pain (28%), and muscle spasms (27%).
- SAEs were reported in 55 patients (53%); the most frequently reported were pneumonia (9 patients; 9%), sepsis, febrile neutropenia (5% each), fall (4%), anemia, and dyspnea (3% each)
- Grade 3 or 4 TEAEs were reported in 102 patients (99%). The most frequently reported Grade 3 or 4 TEAEs were neutropenia (77%), anemia (28%), thrombocytopenia (19%), lymphopenia (14%), and fatigue (12%).

- Infections or infestations were reported in 72% of patients. The most frequently reported were upper respiratory tract infection (28%), pneumonia (15%), sinusitis (14%), and bronchitis (12%).

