### **7.4 Post-Treatment Observation Phase**

For patients who complete all 32 cycles of treatment on study, if have not progressed or started new treatment, patients will be followed with disease evaluations every 90 days (+/- 30 days) until confirmed disease progression or for total duration of 24 months from last EOT visit, whichever comes first, and for OS for up to 10 years from date of enrollment or until death.

Patients who discontinue study treatment before disease progression has been observed, will undergo disease evaluations every 90 days (+/- 30 days) as specified in the Post-Treatment Observation Phase in the Study Calendar for a duration of 24 months or until confirmed hematologic disease progression, whichever comes first.

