#### 8.1.1 Determination of Sample Size

The sample size computations were performed assuming a 5% level of significance and 80% power. The new regimen will be declared effective and worthy of further testing if 8 or more patients have  $\geq$  VGPR among the 40 patients entered into the cohort.

Sample size recommendations for the current design are determined according to A'Hern's exact single-stage phase II design (A'Hern, RP, 2001). We project a  $\geq$  VGPR response proportion of 9%, below which the regimen will be unacceptable, and a  $\geq$  VGPR response proportion of 25%, above which the regimen will be considered worthy of further exploration. The null hypothesis that the  $\geq$  VGPR response proportion is less than or equal to 9% will be tested against the alternative hypothesis that the  $\geq$  VGPR response proportion is greater than or equal to 25%.

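### Section 8.1.7 stops the study for futility at the fifth death, with no cause, window or denominator; read literally, the protocol's own survival figures trigger it before the primary endpoint can be read

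*Combined protocol and SAP*

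**What the plan says.** Section 8.1.7 has two rules. The first sets a limit of 4 deaths; beyond it, "regardless of how many patients have been enrolled at that point or by that time, the study will be stopped due to futility". Under the second, a Grade 3-4 infection rate above 15% puts enrolment on hold while risk-reducing amendments are made. The infection rule is a rate and pauses enrolment. The death rule is a bare count and ends the study.

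No other section narrows the deaths that count. Section 8.1.6 defines OS by death from any cause. Section 7.4 follows patients who complete treatment for progression "and for OS for up to 10 years from date of enrollment or until death". Section 9.1.2 has every death reported as an SAE.

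The primary endpoint is ≥VGPR as best response within 8 cycles. Under Section 8.1.1 the regimen succeeds if at least 8 responders of that depth are counted "among the 40 patients entered into the cohort". The null is a "response proportion of 9%, below which the regimen will be unacceptable" and the alternative a "response proportion of 25%, above which the regimen will be considered worthy of further exploration". No operating characteristics are given for the death rule.

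**The concern.** A futility rule should stop a trial that is unlikely to succeed on its endpoint. This one never looks at response. It counts deaths, which in relapsed/refractory myeloma accumulate from the disease itself even when a regimen is active. The background section reports that on clarithromycin, pomalidomide and dexamethasone a "median OS 19.3 mos was seen". A regimen that only matched that survival would still lose patients steadily during accrual.

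What is at stake is the primary result. If the study stops at the fifth death, the 8-of-40 boundary is applied to a truncated sample or not at all. If the team instead reinterprets the rule during the study, it makes an unplanned decision and departs from the protocol.

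**Working it through.** **1. The plan's own design.** Exact binomial, N = 40, success at 8 or more:
- P(X ≥ 8 | 40, 0.09) = 0.024, against a stated 0.05 or less.
- P(X ≥ 8 | 40, 0.25) = 0.818, against a stated 0.80 or more.

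The design reproduces. Both figures assume that all 40 patients are evaluated.

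**2. Inputs for the death rule.**
- Trigger: the fifth death (Section 8.1.7).
- Response window: 8 cycles × 28 days = 224 days; 224 / 30.44 = 7.36 months.
- Cited relapsed/refractory median OS (Section 1.1): 12.7 months and 16.5 (unit not printed, read as months) for pomalidomide/dexamethasone, 17.5 months for daratumumab alone, 19.3 months for the clarithromycin backbone.
- Optimistic values: 36 months, the overall myeloma figure in Section 1.1, and 60 months, my own assumption.
- Further assumptions: exponential survival; uniform accrual over 12, 24 or 36 months; every death becomes known to the study.

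**3. Deaths within each patient's own first 8 cycles.** With q = 1 − 2^(−7.36 / median OS), expected deaths are 40q and the chance of triggering is P(X ≥ 5 | 40, q).

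| Median OS (months) | q | Expected deaths | P(5 or more) |
|---|---|---|---|
| 12.7 | 0.331 | 13.2 | 0.999 |
| 16.5 | 0.266 | 10.6 | 0.991 |
| 17.5 | 0.253 | 10.1 | 0.985 |
| 19.3 | 0.232 | 9.3 | 0.971 |
| 36 | 0.132 | 5.3 | 0.62 |
| 60 | 0.082 | 3.3 | 0.22 |

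This understates the literal rule, because patients who entered early stay at risk while later ones are treated.

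**4. Staggered entry.** Simulation of 40 uniform entry times plus exponential survival, 100,000 runs per cell. The three values in each cell are for accrual over 12 / 24 / 36 months.

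| Median OS (months) | P(fifth death before last patient completes 8 cycles) | P(fifth death before last patient enrols) |
|---|---|---|
| 12.7 | 1.00 / 1.00 / 1.00 | 0.99 / 1.00 / 1.00 |
| 19.3 | 1.00 / 1.00 / 1.00 | 0.87 / 0.999 / 1.00 |
| 36 | 0.96 / 0.997 / 1.00 | 0.39 / 0.90 / 0.99 |
| 60 | 0.67 / 0.91 / 0.98 | 0.10 / 0.54 / 0.85 |

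The first probability is the relevant one, since the endpoint cannot be read in full until the last patient's window closes. At 19.3 months the fifth death comes at a median of about 9, 13 and 17 months. At that point 31, 23 and 19 patients are enrolled, and only about 6, 10 and 10 are past their 8-cycle window.

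**5. A narrower reading.** For daratumumab with pomalidomide and dexamethasone, Section 1.3.2.2 reports: "Nine deaths (9%) were reported during study treatment or within 30 days after the last dose". That is 9 of 103, of which 6 were due to TEAEs.
- All such deaths: 40 × 9/103 = 3.5 expected; P(X ≥ 5) = 0.27.
- TEAE deaths only: 40 × 6/103 = 2.3 expected; P(X ≥ 5) = 0.08.

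**The case against.** **The rule may have been meant for treatment-period deaths.** It sits beside a toxicity rule. The Schedule of Study Procedures ends adverse event collection 30 days after last treatment, and Section 9.2.1.1 reports SAEs for 30 days after the last dose. On that reading the chance of triggering is 0.27 or 0.08. The reading is plausible, but Section 8.1.7 does not state it. The 30-day window is also not the only candidate, since Section 7.3 monitors for late toxicity for 90 days. What stands is that part of the defect is undefined scope.

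**The survival benchmarks may be too pessimistic.** Where Section 1.1 gives a median number of prior lines for the cohorts with a cited OS, it is five. This trial admits patients after one or more lines and requires a life expectancy of at least 3 months. No OS is cited for daratumumab with pomalidomide and dexamethasone, the closest regimen. This stands too, which is why the tables run to 36 and 60 months. As an extreme check, suppose nobody dies in the first 3 months and the median is held at 19.3 months. With 12-month accrual, the chance of stopping before the last enrolment falls from 0.87 to about 0.53, but the chance of stopping before the primary read stays near 1.00.

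**The DSMC could use judgement.** Section 10 provides for twice-yearly review and lets the committee recommend stopping. It does not override an instruction that the study will be stopped.

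**Conclusion.** The point holds for the rule as written. It has no cause, window or denominator and does not measure futility for a ≥VGPR endpoint. On the literal reading, and at every relapsed/refractory median OS the protocol cites, it fires before the primary endpoint can be read with probability about 1.00. At 36 months the figure is 0.96 to 1.00, and at 60 months 0.67 to 0.98. These results rest on exponential survival and on accrual over 12 to 36 months, neither of which the documents supply.

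A reader might infer that the trial is almost certain to close early, or to close before enrolment is complete. The documents do not support either as fact. The first depends on the literal reading and on survival in more heavily pretreated cohorts. The second fails under longer survival with fast accrual: with 12-month accrual the probability is 0.39 at a 36-month median and 0.10 at 60 months. Nor is the sample-size calculation wrong: its alpha of 0.024 and power of 0.818 hold if all 40 patients are evaluated. An early stop takes that condition away.

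**What to change.** Amend Section 8.1.7 so that the death rule is a safety rule and is no longer labelled futility. State:
- which deaths count;
- over what window, reconciling the 30-day collection and reporting periods (Schedule of Study Procedures, Section 9.2.1.1) with the 90-day monitoring in Section 7.3;
- against what number of treated patients;
- the limit, to be agreed with the DSMC, with the probability of stopping at the death rates the protocol cites.

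If a futility rule is wanted, base it on ≥VGPR. One illustration is a look at 20 patients that stops if 1 or fewer have ≥VGPR: it stops with probability P(X ≤ 1 | 20, 0.09) = 0.45 under the null, and power moves from 0.818 to 0.813 if the look is binding. That look is optional; correcting the death rule does not require it.

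The cost is a wording amendment and a short calculation. There are two downsides. The study would continue past a fifth disease-related death, under the existing twice-yearly DSMC review. Any cause-based count would also rely on investigator attribution in an uncontrolled trial.
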